3.5. End of Study

All Patients: The end of the entire study for all patients is defined as the date on which the last patient remaining on study completes the last study visit/call or when the sponsor decides to end the study. The sponsor reserves the right to terminate the study at any time for any reason (including safety).

Individual Patients: Patients are considered to have completed study participation altogether when they are no longer followed for safety.

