5.2. Cohort 1 (1L Unfit AML Mag+Ven+Aza)

Information for magrolimab is provided in Section 5.1.

The start of the cycle is the first day of azacitidine + venetoclax.

In the event 1 or more components of the study treatment (magnolimab, azacitidine, and/or venetoclax) are discontinued, the following combinations are permitted:

- Magrolimab + azacitidine
- Azacitidine (single agent)
- Venetoclax + azacitidine

The following combinations are not permitted:

- Magrolimab (single agent)
- Venetoclax (single agent)
- Magrolimab + venetoclax

If azacitidine is permanently discontinued, the patient must discontinue the remaining study treatment.

Patients who discontinue study treatment but continue in a response or are achieving clinical benefit will continue to be followed on study for response assessments to ascertain relapse.

When both magrolimab and azacitidine are given on the same visit day, magrolimab will be administered at least 1 hour after the completion of azacitidine administration.

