- Event-Free Survival (Cohorts 1 and 2): EFS is defined as the time from the date of the first dose of study treatment to the earliest date of documented relapse from CR, treatment failure (defined as failure to achieve CR before the fifth cycle of magrolimab+venetoclax+azacitidine in Phase 2 Cohort 1 and before the third cycle of magrolimab + MEC in Phase 2 Cohort 2), or death from any cause. Response assessments post SCT will be included in the analysis. Deaths post SCT or new anti-AML therapies (except SCT and post SCT maintenance) will be included. Those who are not observed to have one of these events during the study will be censored at the date of their last response assessment during the study. Day 1 of treatment will be assigned as the event date for patients with treatment failure.
- Minimal Residual Disease Negative Complete Remission or Complete Remission with Incomplete Hematologic Recovery Rate (Cohort 3): The MRD negative CR/CRi rate is defined as the proportion of patients who maintain CR/CRi as determined by the investigator based on prespecified criteria (Appendix 7) and reach MRD negative disease status on 2 consecutive bone marrow assessments as determined using multiparameter flow cytometry with a sensitivity of < 0.1% while on study prior to initiation of any new anti-AML therapy.
- Relapse-Free Survival (Cohort 3): RFS is measured from the time of the first dose of study treatment until the first date of AML relapse or death from any cause, whichever comes first. Those who are not observed to have relapsed disease or death will be censored at the date of their last response assessment during the study.
- Duration of Minimal Residual Disease Negative Complete Remission (Cohort 3): The duration of MRD negative CR is measured from the time the patient achieves MRD negative status (first of the 2 consecutive MRD negative bone marrow assessments) and maintains CR until the first date of AML relapse, loss of MRD negative status, or death (including assessments post SCT). Those who are not observed to have relapsed disease, loss of MRD negative status, or death will be censored at the date of their last response assessment. If patients start taking new anti-AML therapies (except SCT and post SCT maintenance treatment) before relapse, duration of MRD negative CR will be censored at the last response assessment before the initiation of the new anti-AML therapies.

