- Duration of Minimal Residual Disease Negative Complete Remission or Complete Remission with Incomplete Hematologic Recovery (Cohort 3): The duration of MRD negative CR/CRi is measured from the time the patient achieves MRD negative status (first of the 2 consecutive MRD negative bone marrow assessments) and maintains CR/CRi until the first date of AML relapse, loss of MRD negative status, or death (including assessments post SCT). Those who are not observed to have relapsed disease, loss of MRD negative status, or death will be censored at the date of their last response assessment. If patients start taking new anti-AML therapies (except SCT and post SCT maintenance treatment) before relapse, duration of MRD negative CR + CRi will be censored at the last response assessment before the initiation of the new anti-AML therapies.

- Overall Survival: The OS is measured from the date of the first dose of study treatment to the
 date of death from any cause. Those who are not observed to die during the study will be
 censored at last date they are known to be alive.
- Red Blood Cell Transfusion Independence Rate: The RBC transfusion independence rate is
 the proportion of patients who have a 56-day or longer period with no RBC or whole blood
 transfusion at any time between the date of the first dose and discontinuation of study
 treatment among all patients who are RBC transfusion-dependent at baseline, defined as
 having received an RBC or whole blood transfusion within the 28 days prior to the first dose
 of study treatment (conversion rate), and among all patients who are RBC
 transfusion-independent at baseline (maintenance rate).
- Platelet Transfusion Independence Rate: The platelet transfusion independence rate is the
 proportion of patients who have a 56-day or longer period with no platelet transfusions at any
 time between the date of the first dose and discontinuation of study treatment among all
 patients who are platelet transfusion-dependent at baseline, defined as having received a
 platelet transfusion within the 28 days prior to the first dose of study treatment (conversion
 rate), and among all patients who are platelet transfusion independent at baseline
 (maintenance rate).

The secondary safety endpoint is as follows (Phase 2 cohorts):

 Incidence of treatment-emergent AEs and laboratory abnormalities according to the NCI CTCAE Version 5.0

The secondary PK endpoint is as follows:

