8.5.2. Secondary Analyses

The point estimates of the ORR, CR rate, CR/CRi rate, CR_{MRD} rate, cCR rate, and CR/CRh rate and the corresponding 2-sided exact 95% CIs based on the Clopper-Pearson method will be provided for Cohorts 1 and 2. The analyses of RBC and platelet transfusion independence rates (conversion rate and maintenance rate) will be similar to those of ORR.

Medians, first quartile (Q1), and third quartile (Q3) of EFS distribution, and the proportion of patients who are event free at Weeks 12, 24, and 48 from the first dosing date will be estimated by cohort using the KM method and the corresponding 95% CIs will be reported. Kaplan-Meier plots will be provided. Analyses of OS will be similar to those of EFS.

For the time-to-event endpoints of duration of CR, duration of CR/CRi, duration of CR/CRh, DOR, RFS, duration of MRD negative CR, and MRD negative CR/CRi, analyses will be conducted on the subsets for which the outcome measures are defined. Specifically, the duration of CR, duration of CR/CRi, duration of CR/CRh, and DOR will be based on patients in Cohorts 1 and 2 who achieve CR, CR/CRi, CR/CRh, and OR, respectively. The RFS will be analyzed for Cohort 3, duration of MRD negative CR will be based on patients in Cohort 3 who achieve MRD negative status and maintain CR, and the duration of MRD negative CR/CRi will be based on patients in Cohort 3 who achieve MRD negative status and maintain CR/CRi. The KM method will be used to estimate median durations and 95% CIs, and KM plots will be provided.

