Appendix 10. Amendment History

A high-level summary of this amendment is provided in tabular form in the subsection below. Minor changes such as the correction of typographic errors, grammar, or formatting are not detailed.

Separate summary of change documents for earlier amendments are available upon request.

A separate tracked change (red-lined) document comparing Amendment 5 with this amendment will be made available upon the publication of this protocol.

Amendment 6 (02 November 2023)

Rationale for Key Changes Included in Amendment 6	Affected Sections
The rationale and risk/benefit assessment for the study have been updated to align with the information in Edition 12 of the Investigator's Brochure	Sections 1.6.1, 1.6.2, and 1.8
Long-term follow-up and survival follow-up have been removed as collection of efficacy data after the end-of-treatment (EOT) visit is no longer required.	Sections 3.4, 3.5, 3.6, 5.2, 6.4, 6.12, and Appendix Table 9
Guidance for the use of corticosteroids as premedication for the first few infusions of magrolimab has been incorporated to align with the information in Edition 12 of the Investigator's Brochure.	Section 5.1.4, Appendix Table 4, Appendix Table 5
Guidance for the management of infusion-related reactions has been updated to incorporate the use of corticosteroids as premedication during the first few infusions of magrolimab, and to incorporate guidance for discontinuation of magrolimab in certain cases. This was done to align with the information in Edition 12 of the Investigator's Brochure.	Section 7.8.1.2, Table 15
Toxicity management section for magrolimab has been updated to include guidelines for dose delay and discontinuation in case of severe neutropenia and serious infections to align with the information in Edition 12 of the Investigator's Brochure.	Sections 7.8.1.3 and 7.8.1.4
Event-free survival definition has been updated to align with other studies of magrolimab in patients with acute myeloid leukemia (AML).	Section 8.1.3 and Appendix 7
Contraception appendix has been updated to reflect latest nonclinical embryo-fetal development toxicity data.	Appendix 5
Global Patient Safety (GLPS) has been updated to Patient Safety (PS) to reflect the new department name.	Throughout the protocol, as required

Protocol GS-US-546-5920 amd-6 ELECTRONIC SIGNATURES

Meaning of Signature	Server Date (dd-MMM- yyyy hh:mm:ss)
Clinical Development	02-Nov-2023 20:35:39

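### Sections 8.1.3 and 8.5.2 were not aligned with the current post-treatment schedule; the main harm is response-dependent censoring of Cohort 2 OS after about Week 18

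*Protocol*

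**What the plan says.** **Endpoints (Protocol 8.1.3).** DOR and the durations of CR, CR/CRi and CR/CRh run to relapse or death (DOR also to progressive disease), with post-SCT assessments counted. For EFS, "Response assessments post SCT will be included in the analysis" and "Deaths post SCT or new anti-AML therapies (except SCT and post SCT maintenance) will be included". EFS also dates treatment failure at the start: "Day 1 of treatment will be assigned as the event date for patients with treatment failure". OS is time to death from any cause. "Those who are not observed to die during the study will be" censored at the last date they are known to be alive.

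**Analysis (8.5.2).** Kaplan-Meier quartiles and the "proportion of patients who are event free at Weeks 12, 24, and 48 from the first dosing date" are planned for EFS. OS is to be analysed in a similar way.

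**Data collection.** Section 3.4 lists SCT among the reasons for stopping study treatment. Section 6.4 and Appendix Table 9 place the last response assessment at EOT, followed only by safety contacts 30 and 70 days after the last dose. Section 3.5 adds: "Patients are considered to have completed study participation altogether when they are no longer followed for safety". Section 7.3.3 requires deaths to be reported to 70 days (± 7) after the last dose and does not oblige investigators to seek serious events after that.

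**Cohort 1 (5.2).** Patients off treatment but still in response or benefiting "will continue to be followed on study for response assessments to ascertain relapse". Appendix Table 9 has no visit for this.

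**Background (Appendix 10).** The Amendment 6 entry gives the reason for the schedule: "Long-term follow-up and survival follow-up have been removed as collection of efficacy data after the end-of-treatment (EOT) visit is no longer required". The point does not rest on that entry. The conflict is between sections of the current text.

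**The concern.** Section 8 still describes endpoints that need follow-up after EOT, while Sections 3.4, 3.5 and Appendix Table 9 no longer provide it. A statistical analysis plan can choose a censoring rule, but it cannot supply deaths and relapses that were never collected.

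For OS the gap is more than a wording matter. Kaplan-Meier assumes that patients who leave the risk set have the same future risk as those who stay. In Cohort 2, Section 3.3 takes patients without an objective response off therapy after two cycles, and their observation ends 70 days later. Responders may be treated for up to 12 months. The patients who leave early are those expected to die sooner, so the later part of the OS curve describes mainly responders but is reported as the cohort's survival.

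**Working it through.** **1. Required against collected**

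| Endpoint | Needs | Scheduled |
|---|---|---|
| DOR and durations of CR, CR/CRi, CR/CRh | Relapse or death, including after SCT | Response assessment to EOT; deaths to 70 days after last dose |
| EFS | The same, plus deaths after SCT or new therapy | The same; treatment failure is an event on Day 1 |
| OS, Weeks 12/24/48 and median | Death at any time | Deaths to 70 days after last dose |

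Section 3.4 recommends a 4-week magrolimab wash-out before SCT. If it is followed, 70 days after the last dose is 70 − 28 = 42 days, or 6 weeks, after SCT, with no scheduled marrow in that time.

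**2. Follow-up horizon in Cohort 2** (last dose + 70 days)

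- Stopped at the end of cycle 2: 56 + 70 = Day 126 = Week 18.0. With the +7-day window, Day 133 = Week 19.0.
- Last weekly magrolimab dose on Day 50: 50 + 70 = Day 120 = Week 17.1.
- Last dose on Day 28: Day 98 = Week 14. Last dose on Day 1: Day 71, about Week 10.
- To be observed at a landmark, the last dose must fall on or after: Week 12, 84 − 70 = Day 14; Week 24, 168 − 70 = Day 98 (Week 14); Week 48, 336 − 70 = Day 266 (Week 38).

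Footnote a to Table 2 speaks of leaving the study, where Section 3.3 speaks of leaving therapy. Those passages need reconciling. I have used the reading that gives longer follow-up.

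**3. Size of the OS bias (illustration)**

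The protocol gives no survival by response. Assumptions: exponential survival; 19%, 35% or 55% responders; median OS 3 or 4 months in non-responders and 9 or 12 months in responders (month = 30.44 days); non-responders censored at Day 126. Responders are censored at Day 160 (half, for SCT) or Day 435. Under exponential survival this split does not change the large-sample result.

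Write S_N and S_R for survival in non-responders and responders, and r for the response share.

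- True: S(t) = (1 − r)·S_N(t) + r·S_R(t)
- Kaplan-Meier after Day 126: S(126) × S_R(t)/S_R(126), because only responders remain at risk

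Example with r = 0.35 and medians of 3 and 12 months (91.32 and 365.28 days):

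- S(126) = 0.65 × 0.3843 + 0.35 × 0.7873 = 0.525
- Week 24: true 0.65 × 0.2794 + 0.35 × 0.7270 = 0.436; Kaplan-Meier 0.525 × 2^(−42/365.28) = 0.485
- Week 48: true 0.65 × 0.0781 + 0.35 × 0.5286 = 0.236; Kaplan-Meier 0.525 × 2^(−210/365.28) = 0.353

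Excess of Kaplan-Meier over truth, in percentage points:

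| Responders | Medians (months) | Week 24 | Week 48 |
|---|---|---|---|
| 19% | 3 / 9 | 5.4 | 12.0 |
| 19% | 3 / 12 | 6.1 | 14.6 |
| 19% | 4 / 12 | 5.4 | 14.6 |
| 35% | 3 / 9 | 4.3 | 9.6 |
| 35% | 3 / 12 | 4.9 | 11.7 |
| 35% | 4 / 12 | 4.3 | 11.7 |
| 55% | 3 / 9 | 3.0 | 6.7 |
| 55% | 3 / 12 | 3.4 | 8.1 |
| 55% | 4 / 12 | 3.0 | 8.1 |

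A simulation of 400,000 patients agrees to within rounding. The excess at Week 12 is zero. It is zero throughout if both groups have the same median (5 months was tried). The median is unaffected where survival falls below 50% before Week 18 (the first two rows). In the other seven rows it is 0.3 to 7.6 weeks too long.

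**4. Primary analysis**

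The stated power does not depend on any of this, and it reproduces: Φ[(0.35 − 0.19 − 1.2816·√(0.19 × 0.81/36)) / √(0.35 × 0.65/36)] = Φ(0.959) = 83.1%.

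**The case against.** The strongest reply is that these are secondary, descriptive, single-arm estimates. Section 8.5.1 tests only CR (and MRD-negative CR) against a historical rate, and no OS comparison with the 3-to-5-month background median is planned. The survival inputs above are assumptions, and with 36 patients a 95% interval for a proportion near 49% is about ±16 points, wider than the bias. All of this stands and sets the severity. It does not make the Week 24 and 48 estimates unbiased.

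Several stronger readings are tempting but not supported:

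- *EFS suffers the same bias from non-response.* It does not. Failure to reach CR before the third cycle in Cohort 2 is an event dated Day 1, not a censoring. The exposure of EFS, like that of the durations, lies mainly in responders who stop treatment or go to SCT. No figure has been worked out for it.
- *The durations cannot be computed.* They can. Each definition censors at the last response assessment. The post-SCT clause simply promises data that are not scheduled.
- *Nothing is known after EOT.* Deaths, adverse events and the first new anti-AML therapy are collected to 70 days after the last dose. Follow-up gathered before Amendment 6 may also exist, although the protocol does not say how it would be used.
- *After Week 18 only responders still on treatment are at risk.* Patients who stopped within the previous 70 days are still observed, and Section 3.4 asks sites to try to keep patients who stop dosing in follow-up.
- *Week 18 is a horizon that every patient reaches.* It applies to those who complete two cycles. Earlier stopping shortens it.

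**Conclusion.** The point holds as a misalignment within the current protocol, with one material consequence. Following the plan as written, Cohort 2 OS at Weeks 24 and 48 is censored according to response and is biased upward. So is the median when survival crosses 50% after about Week 18. The direction follows from Sections 3.3 and 3.5 and Appendix Table 9, provided that responders outlive non-responders. The size, about 3 to 6 points at Week 24 and 7 to 15 at Week 48, rests on the assumed survival and is illustrative. There is no bias at Week 12 for patients who complete two cycles. For EFS and the response durations the problem is smaller: the text includes post-SCT assessments for which no visit exists. Cohort 3 enrolled nobody, so it is not affected in practice. A reader might infer that the trial's main conclusion is at risk. It is not, because the CR analysis and its power are unchanged. Should be fixed.

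**What to change.** Choose one of two routes.

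**(a) Align the text with the data.** In 8.1.3, state that response-based events are observed only through EOT and that later deaths count to 70 days after the last dose. Remove or qualify the post-SCT assessment wording. Do not censor at EOT or SCT in a way that discards deaths that are collected. In 8.5.2, either omit Cohort 2 OS at Weeks 24 and 48 and the median, or label them as subject to response-dependent follow-up and show numbers at risk and length of follow-up by response status. Do not assume a common Week 18 cut-off. Cost: wording only, but no unqualified long-term OS statement.

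**(b) Keep the definitions and collect the data.** Obtain vital status, and relapse status where it is on record, once for every treated patient before database lock, as far as consent allows. Cost: one status query per patient, including patients whose participation has already ended.

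Under either route, reconcile the Section 5.2 sentence on continued response follow-up in Cohort 1 with Appendix Table 9.

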4.2. Inclusion Criteria

All Patients

All patients must meet the following inclusion criteria to be eligible for participation in this study:

1) White blood cell (WBC) count $\leq 20 \times 10^3/\mu L$ prior to first dose of study treatment. If the patient's WBC count is $\geq 20 \times 10^3/\mu L$ prior to first dose of study treatment, the patient can be enrolled, assuming all other eligibility criteria are met. However, ensure that the WBC count is $\leq 20 \times 10^3/\mu L$ prior to the first dose of study treatment and prior to each magnolimab dose for the first 4 weeks.

NOTE: Patients can be treated with hydroxyurea and/or leukapheresis throughout the study or prior to first dose of study treatment to reduce the WBC count to $\leq 20 \times 10^3/\mu L$ to enable eligibility for magrolimab dosing.

2) Hb must be ≥ 9 g/dL prior to initial dose of study treatment

NOTE: Transfusions are allowed to meet Hb eligibility (see Section 7.8.1.1).

- 3) Adequate liver function as demonstrated by the following:
 - a) AST $\leq 3.0 \times$ upper limit of normal (ULN)
 - b) ALT $\leq 3.0 \times ULN$
 - c) bilirubin $\leq 1.5 \times \text{ULN}$, or $\leq 3.0 \times \text{ULN}$ and primarily unconjugated if patient has a documented history of Gilbert syndrome or genetic equivalent.
- 4) Patients must have adequate renal function as demonstrated by a creatinine clearance (CLcr) ≥ 30 mL/min calculated by the Cockcroft-Gault formula.
- 5) Patient has provided informed consent.
- 6) Patient is willing and able to comply with clinic visits and procedures outlined in the study protocol.
- 7) Male or female, age \geq 18 years.
- 8) Pretreatment blood cross-match completed (as detailed in Section 6.5.3).
- 9) Male patients and female patients of childbearing potential who engage in heterosexual intercourse must agree to use protocol-specified method(s) of contraception as described in Appendix 5.
- 10) Patients must be willing to consent to mandatory pretreatment and on-treatment bone marrow biopsies (trephines), unless not feasible as determined by the investigator and discussed with the sponsor.

Safety Run-in Cohort 1 and Phase 2 Cohort 1 (1L Unfit AML Mag+Ven+Aza), closed to enrollment globally as of Protocol Amendment 5

In addition to meeting the inclusion criteria for all patients, patients who are enrolled into Safety Run-in Cohort 1 and Phase 2 Cohort 1 must fulfill the following cohort-specific inclusion criteria:

CONFIDENTIAL Page 61 02 November 2023

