5.1.2. Dosage and Administration of Magrolimab

The magrolimab dosing regimen for each safety run-in cohort is presented in Table 1, Table 2, and Table 3. The dose de-escalation regimens for magrolimab in Safety Run-in Cohort 2 are presented in Table 5. Treatment schedules are provided in Appendix 2.

Magrolimab will be administered by IV infusion. The duration of infusion will be 3 hours (\pm 30 minutes) for the first 3 doses of magrolimab, and then 2 hours (\pm 30 minutes) for infusions beyond the first 3 doses. The reduced infusion time to 2 hours is utilized based on prior data demonstrating majority CD47 RO on peripheral blood cells, thus mitigating anticipated RBC toxicities from magrolimab.

During the first 28 days of treatment, WBC count must be $\leq 20 \times 10^3/\mu L$ prior to each magnolimab dose. Patients with WBC $> 20 \times 10^3/\mu L$ can be treated with hydroxyurea (up to 4 g/day) and/or leukapheresis throughout the study to reduce the WBC to $\leq 20 \times 10^3/\mu L$.

Within 24 hours prior to each of the 2 first doses of magnolimab infusion during initial treatment, all patients must have a documented $Hb \ge 9$ g/dL. Patients who do not meet these criteria must be transfused and have their Hb rechecked to meet 9 g/dL prior to each of the first 2 doses of magnolimab.

Hemoglobin must be checked again 3 to 6 hours after the initiation of the first and second doses of magrolimab during initial treatment. The patient should be transfused as clinically appropriate. Investigators should consider additional Hb monitoring during the first week of treatment in patients with symptoms of anemia or at increased risk for complications of anemia.

All patients should be monitored hourly during infusion and for 1 hour after infusion for priming, repriming/re-escalation, and maintenance doses during the first 28 days of treatment. Patients should be monitored (including measurement of vital signs, as clinically appropriate) for signs and symptoms of infusion-related reaction, which have been observed in previous magrolimab studies. Postinfusion monitoring should begin after the infusion is complete. Postinfusion monitoring is not required for doses after Day 22. Patients who experience any treatment-emergent AEs during the observation period should be further monitored, as clinically appropriate.

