5.1.5. Prior and Concomitant Medications: Permitted Concomitant Medications for All Cohorts

For the anti-leukemia regimens administered with magrolimab in this study, the current local or regional prescribing information should be consulted regarding permitted and prohibited concomitant medications.

Live vaccines are prohibited during the study, and for 3 months after the last dose of study treatment {Rubin 2014}.

Premedication, as well as prophylaxis for AEs as described in Sections 5.1.4, 5.2.4, 5.3.5, and 5.4.3, is permitted while on study treatment. Localized non-CNS radiotherapy, erythroid and/or myeloid growth factors, hormonal therapy with LHRH agonists for prostate cancer, hormonal maintenance therapy for breast cancers, and treatment with bisphosphonates RANKL inhibitors are permitted. Red blood cell and platelet transfusions are permitted during screening and prior to enrollment to ensure adequate Hb level, and as per investigator clinical judgment. Blood transfusions are also permitted during the study as clinically indicated for management of cytopenias and should be recorded in the electronic case report form (eCRF) dedicated to transfusions during the study. Hydroxyurea and/or leukapheresis can be used throughout the study to reduce the WBC to $\leq 20 \times 10^3/\mu$ L. In nonclinical studies, co-administration of magrolimab and hydroxyurea in human leukemia engrafted immunodeficient mice did not cause phagocytosis of normal bone marrow cells, suggesting limited on-mechanism toxicity in patients. No gross safety abnormalities were observed in these nonclinical studies. While no formal analyses have been performed, in clinical studies, no significant safety concerns have been observed in patients who have received concomitant magrolimab and hydroxyurea or magrolimab, azacitidine, and hydroxyurea.

All concomitant medications, including all prescription, over-the-counter, herbal supplements, and IV medications and fluids received within 30 days before the first dose of study treatment through the 70-days (\pm 7 days) safety follow-up visit should be recorded in the eCRF.

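### One RBC transfusion given only to reach the 9 g/dL Hb entry limit makes a patient transfusion-dependent at baseline, which probably raises the RBC conversion rate by an amount the protocol cannot supply

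*Protocol*

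**What the plan says.** - **Baseline class (Protocol Section 8.1.3).** A patient is RBC transfusion-dependent after "having received an RBC or whole blood transfusion within the 28 days prior to the first dose" of study treatment. The definition sets no minimum number of transfusions, no Hb trigger and no reason for transfusion.
- **Success (Section 8.1.3).** The rate is "the proportion of patients who have a 56-day or longer period with no RBC or whole blood" transfusion, anywhere from the first dose until study treatment stops. Among baseline-dependent patients it is called the conversion rate; among baseline-independent patients, the maintenance rate.
- **Entry limit (Section 4.2, criterion 2).** "Hb must be ≥ 9 g/dL prior to initial dose of study treatment", with the note "Transfusions are allowed to meet Hb eligibility".
- **Pre-dose rule (Section 5.1.2, repeated in Section 7.8.1.1 and Appendix Table 4, footnote c).** Hb must be documented at 9 g/dL or above within 24 hours before each of the first two magrolimab doses. "Patients who do not meet these criteria must be transfused and have their Hb rechecked to meet 9 g/dL".
- **Screening (Section 5.1.5).** "Red blood cell and platelet transfusions are permitted during screening and prior to enrollment to ensure adequate Hb level". During the study, transfusion is left to clinical indication and recorded on a dedicated eCRF.
- **Analysis (Section 8.5.2).** Both rates are handled like ORR: a point estimate with an exact 95% CI, by cohort, and no test.

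No section excludes transfusions driven by the Hb requirement from the baseline definition.

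**The concern.** The conversion rate is read as the share of patients who came off transfusion support. Under these rules, part of the group from which conversion is counted can be created by the trial itself. The patient is classed while a 9 g/dL requirement is in force and is then judged mostly under usual transfusion practice, so some conversions may need no change in the patient.

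The study has no control arm that would show this component. Section 1.2.3.2 already presents falling RBC transfusion needs in patients dependent at baseline as a favourable feature of magrolimab, so a conversion rate from this study would probably be read in that light. The maintenance rate is affected too, because the same patients are removed from its denominator.

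The problem is specific to RBC. The platelet endpoint has the same form, but Sections 4.2 and 4.3 set no platelet minimum that would prompt an entry transfusion.

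**Working it through.** **1. The plan's own figure.** The protocol states no expected transfusion-independence rate. Its only power figure is for the CR rate in Cohort 2 (Section 8.10: n = 36, 19% versus 35%, one-sided alpha 0.1). By the normal approximation:

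Φ[(0.16 − 1.2816 × √(0.19 × 0.81/36)) / √(0.35 × 0.65/36)] = Φ[(0.16 − 0.0838)/0.0795] = 0.831.

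This matches the stated 83.1% and does not depend on the transfusion definition.

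**2. One patient through the rules.** Take Hb 8.5 g/dL and no other transfusion in the 28 days before dose 1.
- Sections 4.2 and 5.1.2: below 9 g/dL, so the patient is transfused before dose 1.
- Section 8.1.3: that transfusion lies in the 28-day window, so the patient is dependent and is not in the maintenance denominator.
- Section 8.1.3: any later 56-day RBC-free period on treatment makes the patient a conversion. Without one, the patient is a conversion failure.

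A transfusion required before dose 2 (Day 4) comes after baseline. It does not alter the class but restarts the RBC-free count.

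**3. Size of the bias.** Let f be the share of dependent patients who are so only through the Hb requirement, c_entry their 56-day RBC-free rate, and c_true the rate in the other dependent patients.

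Reported conversion rate = (1 − f) × c_true + f × c_entry

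Bias = f × (c_entry − c_true)

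None of the three is in the protocol. With assumed values, the reported rate is:

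| c_true | c_entry | f = 0 | f = 10% | f = 25% | f = 50% |
|---|---|---|---|---|---|
| 20% | 60% | 20% | 24% | 30% | 40% |
| 20% | 80% | 20% | 26% | 35% | 50% |
| 30% | 60% | 30% | 33% | 37.5% | 45% |
| 30% | 80% | 30% | 35% | 42.5% | 55% |
| 40% | 60% | 40% | 42% | 45% | 50% |
| 40% | 80% | 40% | 44% | 50% | 60% |

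At f = 25% the excess runs from 0.25 × (60 − 40) = 5 points to 0.25 × (80 − 20) = 15 points. If c_entry equals c_true, the bias is zero at any f. For the maintenance rate, removing the entry-only patients raises the result if they do worse than patients untransfused at baseline; the protocol does not say whether they do.

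**4. Does a 56-day period fit in Cohort 2?** Section 3.3 stops therapy in patients without an objective response after two cycles, and 2 × 28 = 56 days. On Table 2, magrolimab falls on Days 1, 4, 8, 11, 15, 22, 29, 36, 43 and 50, with the next dose on Day 57. The Cycle 2 Day 28 assessment has a window of ±1 week (Appendix Table 3, footnote j), so it falls between Days 49 and 63. On the planned schedule a non-responder therefore has about 50 to 63 days on treatment. A transfusion on Day 4 moves the earliest qualifying period to Days 5–60. A non-responder would need to be almost free of RBC transfusion through two MEC courses, so conversion in Cohort 2 in practice largely requires a response and continued treatment.

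**The case against.** The strongest reply concerns size and consequence.

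- Many AML patients below 9 g/dL are truly dependent, so f may be modest.
- Mitoxantrone, etoposide and cytarabine cause severe myelosuppression (Sections 7.8.4 to 7.8.6), and magrolimab lowers Hb by about 0.5 to 1.5 g/dL in the first one to two weeks (Section 7.8.1.1). Entry-only patients may then also need transfusion. If conversion mainly follows response, c_entry and c_true may be close.
- The endpoint is one of many secondary endpoints, with no test or decision rule.
- The present definition is objective. Replacing it with an open-label investigator's judgement that a transfusion was given solely for entry could bias the denominator in another way, and would be retrospective for the 18 patients enrolled in closed Cohort 1.

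All of this stands as a limit on size and on the remedy. It does not remove the misclassification, which the protocol fixes in explicit terms and does not leave to the SAP.

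Three stronger readings are tempting and not supported:

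- **That the rate counts patients who never needed transfusion support.** The rules show only that no need was demonstrated beyond the protocol threshold, and such a patient counts as a failure without a 56-day period.
- **That no Hb limit applies once treatment starts.** Section 5.1.2 applies 9 g/dL again before dose 2, and Section 5.1.3 again before the first two doses on repriming.
- **That the excess is large.** A no-effect model with stable Hb and 16 to 24 weeks on treatment can give an excess of 12 to 52 points. Those conditions do not fit Cohort 2, the only cohort still open to enrollment.

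**Conclusion.** The definition lets a transfusion made necessary by the trial's own Hb requirement create the baseline state from which conversion is scored, and it moves those patients out of the maintenance denominator. The bias is f × (c_entry − c_true). It is upward if entry-only patients reach 56 RBC-free days more often than truly dependent patients, which is likely but not shown by the document.

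Its size cannot be derived from the protocol. The 5 to 15 points at f = 25% are an illustration resting on assumed rates, not a forecast, and the bias may be small in Cohort 2. Cohort 1, where treatment continues until discontinuation criteria are met, allows more time for a 56-day period but has only 18 patients; Cohort 3 has none. The primary CR analysis and its power are unaffected. The point matters for what may be concluded from the two RBC rates, and a cheap addition settles it.

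**What to change.** Leave enrollment, dosing and the Hb rules as they are. In Section 8.1.3 keep the present definition and add prespecified conversion and maintenance rates in which a patient whose only RBC transfusion in the 28-day window was given to meet the protocol Hb requirement is not counted as dependent and moves to the maintenance denominator.

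Identify these patients by a stated rule from data already collected: transfusion dates (Section 6.2.1 and the transfusion eCRF in Section 5.1.5) and the Hb recorded before the transfusion. Add a reason field for transfusions recorded from now on. Report the number reclassified and list their pre-transfusion Hb, so that a reader can see who might have been transfused in any case.

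Cost: a sentence or two in Section 8.1.3, one eCRF field and one more row per rate. Downsides: a smaller conversion denominator, a possibly less favourable rate, and some retrospective classification for patients already enrolled. Because the present definition is still reported, nothing is lost.
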